8.2.2 Parts B and C (Food Effect)

A total of 12 subjects will be randomized into Part B and Part C each. To obtain at least 12 evaluable subjects per group for the primary endpoint analysis, every drop-out with incomplete data must be replaced.

The half-width of the 90% confidence interval (CI) will be taken as a measure of precision.

The precision for the T/R ratios to be estimated for AUC and C_{max} for a series of CVs and a fixed sample size of 12 subjects per group is shown in Table 7.

A 2-sided alpha = 0.10 was used in the calculations, and the probability of achieving a pre-defined half-width (precision) was set to 0.80.

Based on these assumptions, the CI half-width for the estimated T/R ratios will be between 9% and 18% for both AUC and C_{max} . Considering the envisaged therapeutic window of tepotinib, this precision is sufficient to meet the study objectives.

Table 7 90% Confidence Intervals for Estimated Test/Reference Ratios, n = 12 per Group

CV	Half-width 90% CI	T/R Ratio	90% LCL	90% UCL
10%	8.8%	0.50	0.46	0.54
		0.75	0.69	0.82
		1.25	1.15	1.36
		1.50	1.38	1.63
15%	13.4%	0.50	0.44	0.57
		0.75	0.66	0.85
		1.25	1.10	1.42
		1.50	1.32	1.70
20%	18.2%	0.50	0.42	0.59
		0.75	0.63	0.89
		1.25	1.06	1.48
		1.50	1.27	1.77

SAS software version 9.4 was used to perform the calculations.

CI = Confidence Interval, CV = Coefficient of variation, LCL = Lower Confidence Limit, R = reference, T = test, UCL = Upper Confidence Limit

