8.6.2 Analysis of Primary Endpoints

Part A

An analysis of variance (ANOVA) model will be fitted for the log-transformed PK parameters C_{\max} , AUC_{0-t} , $AUC_{0-\infty}$ based on the PK analysis set. The model will include treatment, period, sequence and subject within sequence as fixed effects. If a Stage 2 is required and the number of subjects in Stage 2 is sufficiently large, stage will be included as additional effect in the ANOVA model for the analysis of the pooled data of both stages. More details will be given in the SAP.

Treatment differences on the log scale of tepotinib will be estimated for C_{\max} , AUC_{0-t} , $AUC_{0-\infty}$ together with their CIs with coverage probability according to the planned 2-stage procedure in [Figure 3](#). Point estimates and CIs will be back-transformed to the original scale for the comparisons. The variance estimate from Stage 1 will be used to evaluate the power at Stage 1.

The comparison will be the new tablet formulation (TF3) vs the tablet formulation used in clinical studies (TF2) under fasting condition.

Bioequivalence will be assessed after Stage 1 using Stage 1 data, or after Stage 2 using the pooled data of both stages.

The null hypothesis will be rejected if the CI corresponding to the α -level in the [Figure 3](#) (either 90% or 94.12%) for the ratio of the GeoMean lies within the interval 0.8000 to 1.2500.

Parts B and C

A mixed model with treatment, period and sequence as fixed effects and a random effect for subject within sequence will be applied to log-transformed PK parameters C_{max} , AUC_{0-t} , and $AUC_{0-\infty}$ based on the PK analysis set. Treatment differences on the log scale of tepotinib will be estimated for C_{max} , AUC_{0-t} , and $AUC_{0-\infty}$ together with their 90% CIs. Point estimates and CIs will be back-transformed to the original scale for the comparisons:

- Part B: Tepotinib PK parameters after administration of the tablet formulation TF2 under fasting administration vs tepotinib TF2 after a high fat, high calorie breakfast
- Part C: Tepotinib PK parameters after administration of the tablet formulation TF3 under fasting administration vs tepotinib TF3 after a high fat, high calorie breakfast.

Individual estimates of relative bioavailability will be calculated for each subject.

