16.1.1.2 Primary Endpoints in Parts B and C

No hypotheses were defined for Parts B or C.

A mixed model with TREATMENT, PERIOD, SEQUENCE as fixed effects and a random effect for SUBJECT(SEQUENCE) will be applied to log-transformed PK parameters C_{max} , AUC_{0-t} , and $AUC_{0-\infty}$ based on the PK analysis set. Treatment differences Fed-Fasted on the log scale will be estimated for C_{max} , AUC_{0-t} , and $AUC_{0-\infty}$ together with their 90% CIs for each of the tablet formulations TF2 (Part B) and TF3 (Part C) separately. Point estimates and CIs will be back-transformed to the original scale.

Part B: Tepotinib PK parameters after administration of the tablet formulation TF2 under fasting administration vs. tepotinib TF2 after a high fat, high calorie breakfast

Part C: Tepotinib PK parameters after administration of the tablet formulation TF3 under fasting administration vs. tepotinib TF3 after a high fat, high calorie breakfast

Individual estimates of relative bioavailability will be calculated for each subject and descriptively summarized.

The primary endpoints will be descriptively summarized. Scatter plots will be produced for the individual PK parameters by treatment group indicating the geometric means within each treatment group.

The PK variables will also be listed for all subjects of the PK population.

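### Table 7's food-effect precision matches 11 degrees of freedom, but the planned Parts B and C model leaves 10, so at the tabulated CVs it is slightly too favourable

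*Protocol*

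**What the plan says.** Protocol section 8.2.2 justifies 12 subjects in each food-effect part by precision rather than power: "The half-width of the 90% confidence interval (CI) will be taken as a measure of precision". It gives these inputs: "A 2-sided alpha = 0.10 was used in the calculations", and "the probability of achieving a pre-defined half-width (precision) was set to 0.80". Drop-outs with incomplete data are to be replaced: "To obtain at least 12 evaluable subjects per group for the primary endpoint analysis". Table 7 then lists half-widths of 8.8%, 13.4% and 18.2% for CVs of 10%, 15% and 20%, with 90% limits around four illustrative ratios. The text concludes that "the CI half-width for the estimated T/R ratios will be between 9% and 18"% and calls the precision sufficient. Neither the formula nor the degrees of freedom are given; only the software is named.

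The analysis is specified separately. Protocol section 8.6.2 plans "A mixed model with treatment, period and sequence as fixed effects and a random effect for subject within sequence", fitted to the log-transformed parameters. SAP section 16.1.1.2 repeats it: "A mixed model with TREATMENT, PERIOD, SEQUENCE as fixed effects and a random effect for SUBJECT(SEQUENCE"). Protocol section 8.3 allocates subjects 1:1 to two sequences in each part.

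**The concern.** A precision statement should describe the interval that will be computed. A paired t interval from 12 subjects has 11 degrees of freedom because it estimates no period effect. The planned model does estimate one and so has one fewer. If Table 7 rests on 11, the plan promises widths, and a 0.80 probability of reaching them, that its own analysis does not quite deliver. At stake is the accuracy of one table and one sentence that support the sample size of Parts B and C.

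**Working it through.** **Inputs** (protocol section 8.2.2): n = 12; two-sided alpha 0.10, so the t quantile is at 0.95; probability 0.80 of achieving the width; CV 10%, 15%, 20%.

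**Formula.** With within-subject log-scale SD s = sqrt(ln(1 + CV²)), the log half-width reached with probability 0.80 is

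h = t(0.95, df) × sqrt(chi²(0.80, df)/df) × s × sqrt(2/12)

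The percentage half-width is exp(h) − 1. The limits are the ratio divided by, and multiplied by, exp(h). The values of s are 0.09975, 0.14917 and 0.19804.

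**Step 1: reproduce Table 7 with df = 11.** t = 1.7959 and chi² = 14.631, so the multiplier of s is 1.7959 × sqrt(14.631/11) × sqrt(2/12) = 0.8456.

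| CV | h | half-width | Table 7 |
|---|---|---|---|
| 10% | 0.0843 | 8.80% | 8.8% |
| 15% | 0.1261 | 13.44% | 13.4% |
| 20% | 0.1675 | 18.23% | 18.2% |

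All 24 printed limits (3 CVs × 4 ratios × 2) also agree at two decimals. Other standard variants do not reproduce the three rows:

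- 22 df: 8.10 / 12.35 / 16.73%
- 11 df without the 0.80 probability: 7.59 / 11.56 / 15.63%
- normal quantile, without the 0.80 probability: 6.93 / 10.54 / 14.22%
- s set equal to the CV, 11 df: 8.82 / 13.52 / 18.43%
- probability conditional on the interval covering the true value, 11 df: 8.90 / 13.61 / 18.45%

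**Step 2: degrees of freedom of the planned model.** Twelve complete subjects give 24 observations. Subjects take 12 df (absorbing the mean and sequence), treatment 1 and period 1: 24 − 12 − 1 − 1 = 10. In a balanced, complete two-period crossover the treatment contrast is wholly within subject, so treating subject as random does not alter this.

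**Step 3: recompute with df = 10.** t = 1.8125 and chi² = 13.442, so the multiplier is 1.8125 × sqrt(13.442/10) × sqrt(2/12) = 0.8579.

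| CV | h | half-width | difference from 11 df (points) |
|---|---|---|---|
| 10% | 0.0856 | 8.93% | 0.13 |
| 15% | 0.1280 | 13.65% | 0.21 |
| 20% | 0.1699 | 18.52% | 0.29 |

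**Step 4: probability of reaching the printed widths.** For a printed width w, this is P(chi² with 10 df ≤ 10 × [ln(1 + w)/(1.8125 × s × sqrt(2/12))]²). The three chi² arguments are 13.06, 12.98 and 13.02, giving 0.780, 0.775 and 0.777. With 11 df the same check gives 0.800, 0.796 and 0.798, which is the stated 0.80 apart from rounding of w.

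**Step 5: printed limits.** With 10 df, 22 of the 24 limits are unchanged at two decimals. Two change, both at CV 20%: the lower limit at T/R 1.25 is 1.25/1.1852 = 1.055 (1.0547 unrounded), so 1.05 instead of 1.06; the upper limit at T/R 1.50 is 1.50 × 1.1852 = 1.778, so 1.78 instead of 1.77.

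**The case against.** The strongest case against raising this is that nothing turns on it. The shift is at most 0.29 percentage points, 22 of 24 limits stay as printed, and 18% becomes 19% only because 18.52 falls just past the rounding point. Parts B and C are descriptive: protocol section 8.1 plans no hypothesis tests for them, so there is no power or success threshold to miss. The reported intervals will come from the planned model whatever Table 7 says. All of this stands and limits the point to a correction of the text.

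The use of 11 degrees of freedom is also inferred, since the protocol does not state it. That is true, but three half-widths and 24 limits agree with 11, while none of the three printed half-widths agrees with 10.

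A reader might go further and infer that the half-width is the sole basis for 12 subjects, so that the sample size loses its support. The documents do not say that. Protocol section 5.5.1 also attributes the 12 evaluable subjects to guideline advice, and section 8.2.2 treats 12 as fixed and tabulates the precision it gives.

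It can also be said that the CV range matters more than one degree of freedom. It does: Part A assumes a CV of about 24% for Cmax (section 8.2.1), and at 24% the half-width is 22.2% with 11 degrees of freedom and 22.5% with 10. That is a separate question, and any extension of Table 7 would still need the right degrees of freedom.

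**Conclusion.** The point holds as a minor correction. At the CVs in Table 7, the stated precision is slightly too favourable for the planned analysis: 8.8%, 13.4% and 18.2% should read 8.9%, 13.7% and 18.5%, and the printed widths carry a probability of about 0.78 rather than 0.80. This rests on two assumptions: that Table 7 used 11 degrees of freedom, as its numbers indicate, and that each part has 12 subjects with complete data in both periods, which is the protocol's own planning case.

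The result does not show that 12 subjects are too few, that the food-effect estimates or their intervals will be wrong, or that the judgement of sufficient precision would change. Nothing in the documents suggests that 18.5% would be unacceptable where 18.2% is acceptable. It also should not be read as a statement about precision at every CV the protocol considers plausible, because Table 7 stops at 20%.

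**What to change.** Recompute Table 7 with 10 degrees of freedom. The half-widths become 8.9%, 13.7% and 18.5%. At CV 20%, the lower limit for T/R 1.25 becomes 1.05 and the upper limit for T/R 1.50 becomes 1.78; all other limits stay as printed. Restate the summary sentence as a half-width between 9% and 19% for CVs of 10% to 20%, so that the CV range is explicit. Add a note giving the formula and stating that the degrees of freedom are those of the planned crossover model.

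The cost is one table, one sentence and one note. Design, sample size, conduct and planned analysis are unaffected.

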8.3 Randomization

Refer to Section 6.3 for the technical and logistical aspects of treatment allocation.

A total of 40 subjects will be randomized to Part A and 12 subjects each will be randomized to Parts B and C. In each study part, the subjects will be randomized to 1 of 2 sequences at a ratio of 1:1:

- Part A:

Sequence 1: TF3 - TF2

Sequence 2: TF2 - TF3

- Part B:

Sequence 1: TF2 fasted - TF2 fed

Sequence 2: TF2 fed - TF2 fasted

- Part C:

Sequence 1: TF3 fasted - TF3 fed

Sequence 2: TF3 fed - TF3 fasted.

If the PK-variability in Stage 1 of Part A is larger than assumed, additional subjects will be randomized to Part A as required.

A computer-generated randomization scheme will be provided by Nuvisan GmbH CTS Department.

8.4 Endpoints

8.4.1 Primary Endpoints

- Part A: AUC_{0-t} , $AUC_{0-\infty}$ and C_{max} of tepotinib observed from time zero to 168 h post-dose of each period
- Parts B and C: AUC_{0-t} , $AUC_{0-\infty}$ and C_{max} of tepotinib observed from time zero to 168 h post-dose of each period.

8.4.2 Secondary Endpoints

- t_{max} , $t_{1/2}$, apparent total body clearance considering the fraction of dose absorbed (CL/f), and apparent volume of distribution during terminal phase (V_z/f) of tepotinib observed from time zero to 168 h post-dose of each period
- Occurrence of TEAEs (incidence, frequency, intensity and causality), occurrence of changes in safety laboratory assessments, 12-lead ECGs and vital signs.

8.4.3 Exploratory Endpoints

- PK profiles of tepotinib metabolites:

AUC_{0-t} , $AUC_{0-\infty}$, C_{max} , t_{max} , $t_{1/2}$ of tepotinib metabolites observed from time zero to 168 h post-dose of each period

- Genetic variants and mutations in genes that potentially influence PK of tepotinib.

8.5 Analysis Sets

8.5.1 Safety Analysis Set

The Safety analysis set will be defined for each part and will include all subjects who have received at least 1 dose of planned IMP and have had 1 subsequent safety assessment.

8.5.2 Definition of Pharmacokinetic Analysis Set

Part A (Bioequivalence)

The PK Analysis Set for Part A will include all subjects without any relevant protocol deviations with respect to PK and absence of factors likely to affect the comparability of PK results, with adequate trial medication compliance, and who have valid primary endpoints for both treatments.

All PK analyses for Part A will be based on this analysis set.

Parts B and C (Food Effect)

The PK Analysis Set for each Part B and C, will include all subjects without any relevant protocol deviations with respect to PK and absence of factors likely to affect the comparability of PK results, with adequate trial medication compliance, and who have at least 3 post-dose concentration measurements.

All PK analyses for Parts B and C will be based on the respective PK analysis set.

For all Parts (A, B and C)

Subjects in a particular period may be excluded after vomiting or with diarrhea as this could render the plasma concentration-time profile unreliable. The use of a concomitant medication that might interfere with the PK of any investigational drug could be a reason for excluding a subject. Relevant decisions will be made before database lock.

8.6 Description of Statistical Analyses

8.6.1 General Considerations

Statistical analyses will be performed using the computer program package SAS® System for Windows™ (Version 9.4 or later; SAS Institute, Cary, North Carolina, USA).

The results of this trial will be reported using summary tables, figures, and data listings, as appropriate. All data will be summarized by treatment and/or scheduled time point, as appropriate.

For demographic, baseline and safety assessments, continuous measurements will be summarized by means of descriptive statistics (ie number and percentage of observations, number and percentage of missing observations, mean, standard deviation [SD], median, 25th and 75th percentiles, minimum, and maximum) and categorical data will be summarized by means of frequency tables (ie count and percentages), if not stated otherwise.

Concentrations of tepotinib and its metabolites in plasma will be presented in tables and descriptively summarized by treatment and nominal time point using n, arithmetic mean, SD, standard error of the mean, median, minimum, maximum, and CV%. Values below the LLOQ will be taken as zero for descriptive statistics of PK concentrations. Descriptive statistics of PK parameters will additionally show the GeoMean, the geometric coefficient of variation (GeoCV%), and the 95% CI for the GeoMean.

Graphical displays will be given, where appropriate. PK variables will be evaluated and listed for all subjects who provide sufficient concentration-time data. Invalid data will be flagged accordingly.

Missing values will be handled as such and not be replaced by estimates.

Details of the statistical analysis will be described in the statistical analysis plan.

Changes in the conduct of the trial or planned analyses, if any, will be reported in the appropriate section of the statistical analysis plan (SAP) and in the clinical trial report.

8.6.2 Analysis of Primary Endpoints

Part A

An analysis of variance (ANOVA) model will be fitted for the log-transformed PK parameters C_{\max} , AUC_{0-t} , $AUC_{0-\infty}$ based on the PK analysis set. The model will include treatment, period, sequence and subject within sequence as fixed effects. If a Stage 2 is required and the number of subjects in Stage 2 is sufficiently large, stage will be included as additional effect in the ANOVA model for the analysis of the pooled data of both stages. More details will be given in the SAP.

Treatment differences on the log scale of tepotinib will be estimated for C_{\max} , AUC_{0-t} , $AUC_{0-\infty}$ together with their CIs with coverage probability according to the planned 2-stage procedure in [Figure 3](#). Point estimates and CIs will be back-transformed to the original scale for the comparisons. The variance estimate from Stage 1 will be used to evaluate the power at Stage 1.

The comparison will be the new tablet formulation (TF3) vs the tablet formulation used in clinical studies (TF2) under fasting condition.

Bioequivalence will be assessed after Stage 1 using Stage 1 data, or after Stage 2 using the pooled data of both stages.

The null hypothesis will be rejected if the CI corresponding to the α -level in the [Figure 3](#) (either 90% or 94.12%) for the ratio of the GeoMean lies within the interval 0.8000 to 1.2500.

Parts B and C

A mixed model with treatment, period and sequence as fixed effects and a random effect for subject within sequence will be applied to log-transformed PK parameters C_{max} , AUC_{0-t} , and $AUC_{0-\infty}$ based on the PK analysis set. Treatment differences on the log scale of tepotinib will be estimated for C_{max} , AUC_{0-t} , and $AUC_{0-\infty}$ together with their 90% CIs. Point estimates and CIs will be back-transformed to the original scale for the comparisons:

- Part B: Tepotinib PK parameters after administration of the tablet formulation TF2 under fasting administration vs tepotinib TF2 after a high fat, high calorie breakfast
- Part C: Tepotinib PK parameters after administration of the tablet formulation TF3 under fasting administration vs tepotinib TF3 after a high fat, high calorie breakfast.

Individual estimates of relative bioavailability will be calculated for each subject.

8.6.3 Analysis of Secondary Endpoints

Summary statistics will be provided for all secondary PK parameters in plasma by time point.

Graphical displays will be given, where appropriate. Details of the statistical analysis will be described in the SAP.

8.6.4 Analysis of Safety and Exploratory Endpoints

Safety data analysis will be conducted on the Safety Analysis Set of each part. The number and percentage of subjects experiencing at least 1 TEAE will be summarized by treatment as will the number of events. Tables by relationship to study drug and by severity will be generated. AEs will be coded using Medical Dictionary for Regulatory Activities terminology. All laboratory data will be reported with SI units.

Laboratory parameters will be summarized using descriptive statistics for absolute values and change from baseline over time, by post-dose shifts relative to baseline, and data listings of clinically significant abnormalities/out of the normal range.

Vital signs and ECG data will be summarized by changes from baseline values by treatment using descriptive statistics. Clinically significant ECG findings for individual subjects will be listed and summarized as appropriate.

PK concentrations will be descriptively summarized. Individual and mean concentration-timeplots will be produced in linear and log-linear scale.

Exploratory endpoints will be analyzed with descriptive statistics.

8.7

Interim and Additional Planned Analyses

A two-stage design is used in Part A. Based on the measured variability, the corresponding power for the number of subjects in Stage 1 will be estimated. If the power is < 80%, an interim analysis will be performed. The significance level for both the interim analysis and the final analysis will then be set to 0.0294. For details refer to section 8.6.2.

9

Ethical and Regulatory Aspects

9.1

Responsibilities of the Investigator

The Investigator is responsible for the conduct of the trial at the site and will ensure that the trial is performed in accordance with this protocol, the ethical principles outlined in the Declaration of Helsinki, ICH GCP [7], and any other applicable regulations. The Investigator must ensure that only subjects who have given informed consent are included in the trial.

9.2

Subject Information and Informed Consent

An unconditional prerequisite for each subject prior to participation in the trial is written informed consent, which must be given before any trial-related activities are carried out. Adequate information must therefore be given to the subject by the Investigator or an appropriate designee (if local regulations permit) before informed consent is obtained.

A subject information sheet must be prepared in the local language in accordance with ICH GCP [7] and will be provided by the Sponsor for the purpose of obtaining informed consent. In addition to providing this written information to a potential subject, the Investigator or a designate will inform the subject verbally of all pertinent aspects of the trial, using language chosen so that the information can be fully and readily understood by laypersons. The subject will be given sufficient time to read the information and the opportunity to ask questions and to request additional information and clarification.

After the information is provided by the Investigator, the ICF must be signed and dated by the subject and the Investigator. The signed and dated declaration of informed consent will remain at the Investigator's site, and must be safely archived so that the forms can be retrieved at any time for monitoring, auditing and inspection purposes. A copy of the signed and dated information and ICF should be provided to the subject prior to participation.

Whenever important new information becomes available that may be relevant to informed consent, the Investigator will revise the subject information sheet and any other written information to be provided to the subjects and submit them to the IEC for review and opinion. Using the approved revised subject information sheet and other written information, The Investigator will explain the changes to the previous version to each trial subject and obtain new written consent for continued participation in the trial. The subject will be given sufficient time to read the information and the opportunity to ask questions and to request additional information and clarification about the changes.

A separate subject information sheet will be prepared for the PGx testing. The subjects will be informed in the written form and verbally about pertinent aspects of the planned PGx testing including an explanation that this additional examination is mandatory for subjects' participation in this clinical trial. Only subjects who have signed and dated the ICF for PGx testing will be included in this clinical trial.

